13.4 Sample Size

20 subjects will be enrolled with the goal of 15 evaluable subjects who have one month follow-up information available. Although Child-Turcotte-Pugh A and Child-Turcotte-Pugh B7 patients are both included, they will not be analyzed separately.

The next possible step would be a Phase I trial that incorporates the data from HIDA- and functional MRI-guided radiation planning in order to permit dose escalation in liver SBRT as well as the treatment of patients with poor liver function, who are not currently SBRT candidates. As the technique of functionally guided radiation has not been previously used in the treatment of liver

tumors, a 5% relative improvement in functional reserve of the liver will be considered as beneficial. If the use of HIDA scans shows beneficial functional reserve of the liver in at least 3 of 15 of the subjects, this will help encourage further study on the use of HIDA scans for planning. If the true rate of HIDA in improving functional reserve by 5% is at least 30% or higher, we will have 87% probability detecting it with this rule:

True probability HIDA is better than conventional plan by 5%	.1	.2	.25	.3	.4	.5
Probability of seeing at least 3 where HIDA is better	0.18	0.60	0.76	0.87	0.97	≥ 0.99

13.5 Subject Characteristics and Significant Protocol Violations

Baseline subject characteristics will be tabulated, such as demographics (age, race, gender), and disease characteristics (Child-Turcotte-Pugh score, functional liver assessments).

Significant protocol violations such as with respect to eligibility criteria and treatment plan will be tabulated.

13.6 Analysis of Primary Objective

The efficacy set will be used for all the efficacy analysis, unless otherwise noted. For the primary endpoint of difference of functional reserve of liver, the value will be calculated for each subject and described by basic summary statistics. The summary statistics will be displayed overall and by each plan chosen.

13.7 Analysis of Secondary Objectives

The rate at which the plan that utilized the HIDA scan is chosen for the actual treatment will be summarized along with the corresponding exact 95% Binomial confidence interval.

For Local Control, PFS, OS, time to transplant, time to distant liver failure, and time to salvage treatment, the median and the corresponding two-sided 95% confidence intervals will be calculated using the Kaplan-Meier method. Estimates and 95% confidence intervals will also be provided for 6 and 12 months. Local control will be evaluated using RECIST 1.1 criteria.

Changes in liver function tests using HIDA scans, standard blood tests and CTP score will be calculated and summarized. Additionally, all safety data will be listed. For the treatment-emergent AEs, namely AEs started or worsened during the on-treatment period, the incidence will be summarized by system organ class and/or preferred term, severity based on CTCAE grades, type of adverse event and the relation to the study drug. Deaths reportable as SAEs and non-fatal serious adverse events will be listed by and tabulated by type of adverse event. This will be done with the safety set.

Changes in liver volume in the treated and untreated segments will be summarized by basic summary statistics.

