Hepatobiliary tumors globally are the fifth-most common cause of cancer and the second leading cause of cancer death.[1] In the United States in 2015, there are expected to be 46,570 hepatobiliary malignancies with 28,250 deaths. Hepatocellular carcinoma (HCC) is the most common type of hepatobiliary tumor. The primary risk factors for HCC are chronic hepatitis B and C infections, although cirrhosis of any cause increases the risk. The rising incidence of hepatitis C has caused HCC to become one of the fastest-growing cancers in terms of incidence and death in North America.[1] Surgical resection and liver transplantation offer the best outcomes, with 5-year overall survival (OS) rates of 50-85%.[2-5] Unfortunately, many HCC patients are not candidates for surgical resection due to the presence of locally advanced disease or medical comorbidities. In addition, only select patients with early stage HCC (tumors <5 cm) are candidates for liver transplantation.[6] For patients who are not surgical candidates or who refuse surgery, a variety of nonsurgical treatment modalities are available, including radiofrequency ablation (RFA), transarterial chemoembolization (TACE), radioembolization (Y-90), chemotherapy (primarily sorafenib-based), and radiation therapy (RT). TACE, RFA, and RT can be used as “bridging” therapies to prevent disease progression in patients awaiting transplantation. However, to date, there have been no randomized trials comparing these modalities. A discussion at a multidisciplinary tumor board where physicians from each respective specialty of surgery, interventional radiology, radiation oncology, hepatology, and radiology often determines which modality is pursued. Similarly, the other hepatobiliary tumors, namely cholangiocarcinoma and gallbladder cancer, are primarily treated with surgery if possible. An additional indication for focal liver radiation therapy exists in patients with oligometastases from certain primary malignancies, such as colon, lung, or breast cancer.

Historically, the use of radiation in cancers of the liver was limited due to the risk of radiation-induced liver disease (RILD), which is characterized by anicteric ascites and elevated transaminase levels. No standard method of reversing RILD is known, and it can lead to fatal liver failure. The risk

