4.2 Secondary Objectives

1. To assess the rate at which the theragnostically planned radiation plan is chosen as the actual treatment plan instead of the conventionally planned radiation plan.
2. To collect data regarding local control (LC), progression free survival (PFS), overall survival (OS), time to transplant (TT), distant liver failure, and salvage therapy in patients undergoing functional image-guided planning for liver SBRT. To document patterns of failure so that local failure versus distant liver failure can be accounted for.
3. To assess treatment toxicity.

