4.5 Secondary Endpoints

1. The rate at which the theragnostically planned radiation plan is chosen as the actual treatment plan rather than the conventionally planned radiation plan.

2. LC, PFS, OS, time to transplant, distant liver failure, and time until salvage treatment
3. Post treatment changes in liver function tests and CTP score. We plan to document the rate of decline of CTP class as well as the rate of any grade of hepatic toxicities.

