5.0 ELIGIBILITY CRITERIA

5.1 Inclusion Criteria

1. Subjects must be ≥ 18 years of age at the time of signing informed consent
2. Diagnosis of primary liver malignancy (including hepatocellular carcinoma [HCC] or cholangiocarcinoma) or liver metastasis from any primary solid tumor site by characteristic imaging findings on CT or MRI, clinical presentation, and/or pathologic confirmation of diagnosis. Subjects with other current or prior malignancies are eligible for this study.
3. Patients with liver metastases must have at least one of the following clinical factors that may affect liver function:
 - a. History of liver resection (at any time)
 - b. History of cirrhosis (any cause), fatty liver disease, or hepatic insufficiency due to any cause
 - c. Prior radiation to the upper abdomen including radioembolization
4. ECOG (Zubrod) Performance Status 0-2.
5. Subjects must have a Child-Turcotte-Pugh (CTP) score ≤ 7 to be eligible.
6. Patients who have been previously treated with non-SBRT liver directed therapies may be enrolled on study. At least 3 months must have elapsed between the most recent liver-directed therapy and study entry.
7. Ability to provide written informed consent and HIPAA authorization
8. Subjects with an allergy to contrast agents may be enrolled at the treating physician's discretion with appropriate pre-treatment and symptom management.

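### Section 13.7 plans only Kaplan-Meier for local control, transplant, distant liver failure and salvage; if death or transplant is censored, 1-KM at 6 and 12 months will exceed the true cumulative incidence.

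*Combined protocol and SAP*

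**What the plan says.** Section 4.5 lists the outcomes by name only: "LC, PFS, OS, time to transplant, distant liver failure, and time until salvage treatment". Section 13.7 puts all of them under one estimator. Its list ends "and time to salvage treatment, the median and the corresponding two-sided 95% confidence intervals will be calculated using the Kaplan-Meier method", and it adds: "Estimates and 95% confidence intervals will also be provided for 6 and 12 months". The only definitional statement there is "Local control will be evaluated using RECIST 1.1 criteria". Appendix 1 reproduces the response criteria but says nothing on time origin or censoring.

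No section gives an event list, a time origin, or a rule for subjects who die or are transplanted before the event. Section 13.1 rules out imputation of missing data, which does not settle the matter. Cumulative incidence, or any other competing-risk method, appears nowhere in the document.

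The documents expect both competing events. Section 2.0 lists radiation among the bridging "therapies to prevent disease progression in patients awaiting transplantation". Time to transplant is itself a secondary endpoint. Section 2.0 also describes four patients with progressive liver dysfunction in the cited phase I/II HCC trial: two were transplanted and two died of liver failure.

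**The concern.** Kaplan-Meier censoring assumes that a censored subject could still have the event later, at the same rate as those still followed. A subject who has died cannot have local failure, distant liver failure, salvage or transplant. A subject whose treated liver has been removed cannot have local or distant failure in that liver. If such subjects are censored, 1-KM estimates the risk in a hypothetical setting without death or transplant. It is then at or above the proportion of enrolled subjects who have the event.

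The direction depends on how the result is expressed. The incidence of local failure, distant liver failure, salvage and transplant is overestimated. Local control, reported as a control rate, is underestimated.

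At stake is the reading of the 6- and 12-month rates. Section 4.2 sets the aim "To document patterns of failure so that local failure versus distant liver failure can be accounted for". That is a question about the share of subjects failing in each way, which is what cumulative incidence describes.

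**Working it through.** **The plan's own figure.** The plan states no expected rate for these outcomes. Its only design figure is the 0.87 in Section 13.4, the chance of at least 3 of 15 at a true rate of 30%. The exact binomial tail gives 0.873, so it reproduces. It concerns the primary endpoint and does not depend on anything below.

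**Inputs.**
- Two-year local control of 93% (liver metastases) and 74% (HCC), from the trials cited in Section 2.0, read here as net rates with a constant hazard.
- 12-month net risks of death and transplant: not in the documents. Assumed pairs are 15% and 0%, 30% and 15%, 45% and 30%.

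**Formulas**, with time t in years, event hazard h and total competing hazard c, each hazard being -ln(1 - 12-month risk):
- 1-KM with competing events censored: 1 - exp(-h·t)
- Cumulative incidence: h/(h+c) × [1 - exp(-(h+c)·t)]

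**12-month local failure.** 1 - √0.93 = 3.6% and 1 - √0.74 = 14.0%.

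**One case in full** (74% control, 45% death, 30% transplant): h = 0.1506 and c = 0.5978 + 0.3567 = 0.9545, so h + c = 1.1051. Cumulative incidence = 0.1363 × (1 - 0.3312) = 9.1%, against a 1-KM of 14.0%. The gap is 4.9 points.

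| 12-month 1-KM | Death 15%, transplant 0% | Death 30%, transplant 15% | Death 45%, transplant 30% |
|---|---|---|---|
| 3.6% | 3.3% (gap 0.3) | 2.8% (0.8) | 2.3% (1.3) |
| 14.0% | 12.9% (1.1) | 11.0% (3.0) | 9.1% (4.9) |
| 20% (assumed) | 18.5% (1.5) | 15.8% (4.2) | 13.1% (6.9) |
| 40% (assumed) | 37.2% (2.8) | 31.9% (8.1) | 26.8% (13.2) |

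Cells give the cumulative incidence, with the gap in percentage points. The last two rows show what happens for outcomes with higher event rates; no rate for them is given in the documents. At 6 months (t = 0.5) the local-failure gaps shrink to 0.1-0.3 points in the first scenario and 0.4-1.5 in the third.

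For time to transplant, only death competes. With an assumed 20% transplant and 30% death at 12 months, 1-KM is 20.0% and the cumulative incidence 16.9%.

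**Invented 15-subject example.** Competing events fall at months 2, 4, 7 and 8, and local failures at 5.5, 11 and 11.5. The numbers at risk at the failures are 13, 10 and 9. KM = 12/13 × 9/10 × 8/9 = 73.8%, so 1-KM is 26.2%. Yet 3 of 15 subjects failed, which is 20.0%. As a control rate, 73.8% is reported although 80.0% had no local failure.

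**The case against.** The strongest objection is that the plan never says death or transplant is censored. If death were counted as an event, 1-KM would be a valid estimate of that composite. This stands, and it makes the finding conditional: a reader might infer that the planned rates are certain to be overstated, but the documents do not support that. The objection does not remove the point. Censoring is the usual practice for a single event type, and a composite with death would no longer be local control or time to transplant.

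A reader might also infer a large bias from a scenario such as 40% failure at 12 months. For local control this conflicts with the plan's own background. Under a constant hazard, 40% at 12 months means 36% two-year control (0.6 × 0.6), against the cited 74-93%.

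Precision limits the practical effect. One subject in 15 is 6.7 points, and an exact 95% interval for 3 of 15 runs from 4.3% to 48.1%. These are descriptive secondary outcomes of a pilot with no test or decision rule attached. That bears on priority, but it does not justify a systematic error that is cheap to avoid.

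Two further inferences are not supported as required changes. Section 2.0 says "only select patients with early stage HCC (tumors <5 cm) are candidates for liver transplantation", and Section 5.1 admits cholangiocarcinoma and metastases, so a reader might want the transplant curve restricted to candidates. The proportion transplanted among all treated subjects is still a valid description. Nor do the cited control rates show that a median cannot be reached: that extrapolates from other trials, and a median reported as not reached is ordinary output.

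**Conclusion.** The point holds in conditional form. Kaplan-Meier is the only method planned for four outcomes that death can preclude, two of which transplant can also preclude. If those subjects are censored, 1-KM overestimates the cumulative incidence of all four, and Kaplan-Meier understates the proportion without local failure. A reader who concludes that local control itself would look too good has the direction reversed.

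The size is uncertain because it rests on constant hazards, on two-year control borrowed from other trials, and on assumed death and transplant risks. On that basis the 12-month gap for local failure ranges from 0.3 to 4.9 points across the scenarios. It grows with the event rate and is zero without competing events. The change is worth making, but it does not affect the primary endpoint or the 3-of-15 rule.

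**What to change.** In Section 13.7:
- Keep Kaplan-Meier for OS and PFS, stating that death is a PFS event.
- For local failure, distant liver failure, salvage and transplant, report Aalen-Johansen cumulative incidence with 95% confidence intervals at 6 and 12 months.
- Name death as a competing event for all four, and transplant as a competing event for local and distant liver failure.
- State whether a transplant counts as salvage or competes with it; salvage is not defined at present.
- Give the event and time origin for each outcome.

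Medians may stay, and time to transplant may stay on the full efficacy set. The cost is SAP wording and a standard software routine.

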5.2 Exclusion Criteria

1. Subjects who are pregnant or planning to become pregnant during the study. Women of child bearing potential must have a negative pregnancy test
2. Subjects must not have received chemotherapy within 2 weeks of planned 1st day of RT.
3. No more than 3 lesions may be treated. The maximum sum of the diameter(s) of the lesion(s) must be ≤ 6 cm
4. Uncontrolled intercurrent illness including, but not limited to, ongoing or active infection (or infections requiring systemic antibiotic treatment), active upper GI ulceration or hemorrhage, symptomatic congestive heart failure, unstable angina pectoris, cardiac arrhythmia, or psychiatric illness/social situations that would in the opinion of the investigator limit compliance with study requirements

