8.5 Follow up

Follow up visits will occur at 3, 6 and 12 months (+/-30 days) post the end of treatment visit.

Subjects will have the following procedures at this visit:

1. Physical Exam
2. Vitals
3. ECOG performance status
4. Laboratory Assessments (CBC with differential, CMP, INR +/- AFP or CEA as indicated)
5. Clinical assessment of toxicity
6. Triple-phase CT or eovist MRI
7. HIDA scan

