9.4 Radiation Planning

Standard Target Contouring guidelines

1. GTV is contoured based on CT obtained during simulation and any previous CT, MRI, or PET scans.
2. The internal target volume (ITV) will account for tumor motion as seen on 4D-CT. Viewing the lesion on individual phases may be necessary in order to adequately delineate the lesion.
3. The planning target volume (PTV) will account for set-up error and will be created by expanding the ITV 1 cm cranio-caudally and 0.5 cm radially, unless less motion can be documented on simulation scans.

Contouring from the HIDA scan

1. Based on the HIDA scan data, contours of relative functional liver will be created based on the following thresholds of maximum intensity: 0-25% maximum, 25-100% maximum, 50-100% maximum, 75-100% maximum. These structures will serve as avoidance structures in the design of radiation fields for theragnostic SBRT planning.

Standard SBRT

The standard SBRT prescription, planning, constraints, and treatment parameters are as follows:

1. Prescription:
3- or 5-fraction SBRT will be utilized in this study depending on clinical scenario. It is recommended that subjects without cirrhosis or with CTP A disease are treated with 3 fractions and those with CTP B cirrhosis are treated with 5 fractions. The dose range typically will be from 4000-5400 cGy delivered over 3-5 fractions.
2. Planning:
SBRT; IMRT if constraints not met or for additional functional sparing.

3. SBRT Constraints:

Structure	Volume	Dose / Constraint
PTV	>95%	Rx
GTV	>98%	>110% Rx
Liver – GTV	700cc or V10 Gy	<1500cGy or <70%
	1/3 uninvolved	<1000cGy (CTP-A), <1800cGy (CTP-B7)
	500cc uninvolved	<700cGy (CTP-A), <1200cGy (CTP-B7)
Duodenum	0.5 cc	2400 cGy (3 fraction) 3000 cGy (5 fraction)
	<5 cc	1650 cGy (3 fraction) 1800 cGy (5 fraction)
	<10 cc	1140 cGy (3 fraction) 1250 cGy (5 fraction)
Stomach	0.5 cc	2250 cGy (3 fraction) 3000 cGy (5 fraction)
Esophagus	0.5 cc	32 Gy (5 fx)
Spinal Cord	100%	<600cGy/fraction
Chest Wall	.5 cc	<5000cGy (5 fraction)
	<5cc	4000cGy (3 fraction)
	<30cc	3000cGy
R Kidney	2/3	<2000cGy
L kidney	1/3	<1500cGy
Heart	0.5 cc	3000 cGy (3 fraction) 5250 cGy (5 fraction)

a. Variation acceptable constraints (per RTOG 1112)

Structure	Variation acceptable	Deviation unacceptable
Esophagus max (0.5 cc)	>32 but ≤34 Gy	>34 Gy
Stomach max (0.5 cc)	>30 but ≤32 Gy	>32 Gy
Duodenum max (0.5 cc)	>30 but ≤32 Gy	>32 Gy
Small bowel max (0.5 cc)	>30 but ≤32 Gy	>32 Gy
Large bowel max (0.5 cc)	>32 but ≤34 Gy	>34 Gy

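### Local control is judged by whole-patient RECIST 1.1 with no treated-lesion rule, so growth of one of several treated lesions can be missed and, read literally, out-of-field liver disease counts as local failure

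*Combined protocol and SAP*

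**What the plan says.** Section 13.7 plans Kaplan-Meier medians, with estimates at 6 and 12 months, for local control and for several other endpoints. Its whole definition of local control is one sentence: "Local control will be evaluated using RECIST 1.1 criteria".

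Section 4.2 gives the aim: "To document patterns of failure so that local failure versus distant liver failure can be accounted for". Section 4.5 lists the endpoints separately: "LC, PFS, OS, time to transplant, distant liver failure, and time until salvage treatment". No section defines a local-control event or a distant liver failure, or ties either to the treated lesion or the PTV.

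On treated lesions, Section 5.2 says "No more than 3 lesions may be treated" and "The maximum sum of the diameter(s) of the lesion(s) must be" at most 6 cm. Section 8.5 schedules "Triple-phase CT or eovist MRI" at 3, 6 and 12 months.

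The only RECIST text is Appendix 1. In summary:
- At most two target lesions are taken per organ, chosen by size, organ representation and reproducibility. Whether a lesion was irradiated plays no part.
- Progression on targets needs a rise of 20% and 5 mm in the summed diameters over the smallest sum on study.
- Other lesions are non-target and need not be measured. Modest growth in them usually does not count, but unequivocal progression does.
- Any new lesion is progression.

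**The concern.** Appendix 1 describes the patient's total disease. Local control after SBRT is about the irradiated lesions. Using the first to measure the second can go wrong in two directions.

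- **Missed local failure.** One treated lesion can grow while the sum stays under the threshold, because another target dilutes or offsets it. A third treated lesion in the liver is necessarily non-target and outside the sum. The non-target test then asks whether overall burden would justify stopping therapy, which has no clear meaning months after a 3- or 5-fraction course has ended.
- **False local failure, on a literal reading.** A new liver lesion away from the treated volume is progression, and so would be a local-control event with every treated lesion controlled.

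Section 3.0 makes preserving tumour control part of the study's goal, and local control is the listed endpoint closest to it. A failure missed at the 6-month scan is next looked for at 12 months, so both planned time-point estimates could be affected.

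**Working it through.** The plan gives no figure for local control to reproduce. Its one probability table (Section 13.4) concerns the primary 3-of-15 rule. The exact binomial tail at a true rate of 0.30 is 0.873, against the stated 0.87, and has no bearing here.

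**Inputs.** From Section 5.2: up to three treated lesions, total diameter at most 60 mm. From Appendix 1: at most two liver targets; progression at +20% and +5 mm in the sum. The individual lesion sizes below are assumptions within the 60 mm limit, and baseline is taken as the smallest sum.

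**Growth needed in one target, the other stable.** With target sum S and own diameter a:
- sum rule: max(5, 0.2 × S) mm
- own-diameter rule: max(5, 0.2 × a) mm

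| Sum S | Growing lesion a | Sum rule | Own-diameter rule |
|---|---|---|---|
| 60 mm | 20 mm | 12 mm (60%) | 5 mm (25%) |
| 60 mm | 30 mm | 12 mm (40%) | 6 mm (20%) |
| 40 mm | 20 mm | 8 mm (40%) | 5 mm (25%) |

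**Worked cases.**
1. Dilution: 40 + 20 = 60 becomes 40 + 30 = 70. Change 10/60 = +16.7%, not progression. The growing lesion changed by 10/20 = +50%.
2. Offset: 20 + 20 = 40 becomes 26 + 14 = 40. Change 0%, although one lesion gained 6 mm (+30%).
3. Third treated lesion: 25, 20 and 15 mm, with the two largest as targets (sum 45). The third going from 15 to 21 mm is +6 mm, 6/15 = +40%. The target sum stays at 45, a change of 0%. Only a judgement of unequivocal non-target progression could register it.
4. New lesion outside the treated volume, all treated lesions stable: the sum changes by 0%, yet the new-lesion rule makes it progression.
5. Single treated lesion as the only target: 20 becomes 30, +50% and +10 mm. Both rules call progression, so nothing is missed. Only case 4 can arise in such a subject.

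**The case against.** The strongest reply is that the out-of-field problem rests on an unnatural reading. Local control, PFS and distant liver failure are listed separately, and Section 4.2 wants local and distant failure told apart. An analyst would probably take RECIST 1.1 as supplying thresholds and local as confining them to the treated site. That largely stands: the false-failure direction is a missing sentence, and a reader should not infer that the sponsor planned to count distant disease as local failure.

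It does not rescue the other direction. Even with local confined to treated lesions, the sum rule still gives +16.7% in case 1, and the third lesion is still outside the sum.

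A second reply is that the data would allow repair. Appendix 1 has target diameters recorded at each evaluation and keeps new lesions in a separate column, and Section 13.1 permits further exploratory analysis. This is fair for up to two treated targets. It fails for a treated lesion classed as non-target, which may have no recorded diameter unless scans are re-read. A rule applied afterwards without being written down is also hard to reproduce.

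Third, the examples are unfavourable ones. The 12 mm figure needs a target sum at the 60 mm limit, the 0% case needs opposite changes, and unequivocal progression can still catch a third lesion. So growth can be missed; it is not always missed.

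A reader might also infer that untreated liver lesions will often occupy the target slots, since "Patients who have been previously treated with non-SBRT liver directed therapies may be enrolled on study" and nothing requires every liver lesion to be treated. The documents permit this but give no reason to expect it.

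**Conclusion.** The concern holds in a limited form. As stated, the rule can miss growth of one of several treated lesions. Read literally, it also counts new out-of-field liver disease as local failure; the endpoint listing suggests that was not intended, but no section says so.

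The size per case is as shown: a 20 mm lesion beside a stable 40 mm one must grow 60% before the sum triggers, against 25% on its own diameter. These sizes are illustrative. The documents do not give the number of lesions per subject, so the frequency of misclassification cannot be estimated, and it would be wrong to infer a known bias in the local-control estimates. For scale, one misclassified event shifts a crude proportion by 1/20 = 5 to 1/15 = 6.7 points.

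Local control is a secondary, descriptive endpoint in a pilot. A reader might infer that the trial's main conclusion is at risk; it is not, because the primary endpoint and the 3-of-15 rule do not use local control. The change is still worth making, because the stated rule can give a wrong answer and a better one is cheap.

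**What to change.** In Section 13.7, replace the single sentence with a treated-lesion definition:
- Measure every treated lesion (up to three) at each scheduled scan, whether or not it is a RECIST target.
- Call local failure when a treated lesion's own longest diameter has grown by 20% or more and by 5 mm or more over its own nadir, or when new tumour appears within the PTV. The PTV already exists for each subject; Section 9.4 forms it by "expanding the ITV 1 cm cranio-caudally and 0.5 cm radially", unless less motion is documented.
- Define patient-level local control as time to the first local failure in any treated lesion.
- Count other new or growing liver lesions as distant liver failure.
- Keep whole-patient RECIST 1.1 for PFS.

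The cost is SAP wording, one extra diameter per existing scan when three treated lesions compete for two liver target slots (more only if untreated lesions take those slots), and some time relating new lesions to the PTV in about 15 to 20 subjects. No new imaging is needed. Local control could no longer be read directly from the patient-level RECIST assessment.

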Significant variability in liver function is present in the population of patients with liver tumors and cirrhosis. Different models for grading the severity of cirrhosis are available, including the Child-Turcotte-Pugh (CTP) and Model for End-Stage Liver Disease (MELD) score. To date, CTP score has been the preferred scoring system in evaluating patients for consideration of SBRT. There are other staging and prognostic scores for patients with HCC including the AJCC stage, BCLC stage, CLIP score, and ALIBI score. The CTP score is based on the levels of bilirubin, albumin, and PT/INR; it also incorporates a subjective grading system for ascites and encephalopathy. The range of scores is 5 to 15, with scores 5-6 classified as CTP A, 7-9 CTP B, and 10-15 CTP C.[13] The risk of side effects has been suggested to increase with higher CTP scores. In the study by Choi et al, 75% of their patients had CTP A disease, and there were no grade 3 toxicities reported in their trial. [11] One-third of patients in the phase I/II trial at Indiana University experienced grade 3 hematologic or hepatic toxicity, although 17 out of 21 of those patients had pre-treatment grade 2 dysfunction in that category. In addition, there were 4 patients who had progressive liver dysfunction, 2 of whom went on to liver transplantation and the other 2 who died as a result of liver failure. All 4 of these patients had CTP \geq B8, and 2 of those patients were treated with 42 Gy in 3 fractions, which was concluded to be unsafe in CTP B patients.[10]

In addition to baseline liver dysfunction, many of the patients who are referred for liver SBRT have had prior therapies such as surgical resection, chemotherapy, RFA, TACE, or conventional radiotherapy, which can adversely affect liver function. A recent retrospective study from Michigan comparing their institutional experience of SBRT with RFA found that patients who were treated with SBRT were more likely to have received prior liver-directed therapies with a median of 2 treatments in SBRT patients compared to 0 in RFA patients.[14]

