13.0 STATISTICAL METHODS

13.1 General Considerations

Statistical analysis of this study will be the responsibility of the Department of Biostatistics at Indiana University School of Medicine. Parameter estimates and relevant summary statistics will be reported for both efficacy and safety outcomes. Continuous variables will be summarized by means, medians, minima, maxima and standard deviations. Categorical variables will be summarized by frequencies and percentages. Missing data will not be imputed. Additional exploratory analysis will be conducted when appropriate. Changes from the analysis plan will not require an amendment to the protocol unless it changes a significant feature in the protocol. The statistical analysis methods are outline below.

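### The rate of CTP class decline has no denominator and no rule for death or transplant, so an available-case summary could make liver safety look better than it was

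*Combined protocol and SAP*

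**What the plan says.** Secondary endpoint 3 (section 4.5) covers post-treatment change in liver function tests and CTP score, and it promises a rate: "We plan to document the rate of decline of CTP class as well as the rate of any grade of hepatic toxicities".

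The analysis in section 13.7 is one sentence: "Changes in liver function tests using HIDA scans, standard blood tests and CTP score will be calculated and summarized". The general rule in section 13.1 is "Missing data will not be imputed".

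On timing, section 8.5 states "Follow up visits will occur at 3, 6 and 12 months (+/-30 days) post the end of treatment visit". Blood tests and HIDA are due at those visits. Blood tests are also due midway through radiation and about 30 days after it. The study calendar (section 10.0) marks CTP scoring only at baseline and midway.

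Section 13.7 estimates overall survival and time to transplant separately by Kaplan-Meier, and lists safety data. Section 12.0 names death as a reason for leaving the study. None of these places connects death or transplant to the CTP decline rate.

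**The concern.** Deteriorating liver function can end in death or transplant, and after either event the subject's own liver can no longer be measured. The missing values are therefore related to the outcome. The Background (section 2.0) shows that the pathway is real. In the institution's earlier phase I/II trial, "there were 4 patients who had progressive liver dysfunction, 2 of whom went on to liver transplantation and the other 2 who died as a" consequence of liver failure.

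If the summary uses only available values, two things can happen. A subject who dies of liver failure with no decline yet recorded adds nothing to the numerator. A transplanted subject may contribute graft values that look like improvement, since nothing excludes them. Both errors point towards apparent safety. They affect the CTP decline rate and the mean HIDA, laboratory and CTP changes at 3, 6 and 12 months. Section 13.4 names dose escalation and treatment of patients with poor liver function as the possible next step, and a liver-decline rate is a figure readers would consult for that.

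**Working it through.** **The plan's own figure.** The only computed design figure is in section 13.4 and concerns the primary endpoint: "If the use of HIDA scans shows beneficial functional reserve of the liver in at least 3 of 15 of the subjects", with "we will have 87% probability detecting it with this rule" at a true rate of 30%.

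P(X ≥ 3 | n = 15, p = 0.3) = 1 − [0.7^15 + 15(0.3)(0.7^14) + 105(0.09)(0.7^13)] = 1 − (0.0047 + 0.0305 + 0.0916) = 0.873.

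This agrees with the stated 87%. The other five columns also reproduce (0.184, 0.602, 0.764, 0.973, 0.996). Nothing in the present point changes them.

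**Inputs for the decline rate.**
- n = 20 or 15, from section 13.4: "20 subjects will be enrolled with the goal of 15 evaluable subjects who have one month follow-up information available". I assume all n are treated.
- d = subjects with a recorded CTP class decline. This is an assumption, because the documents give no rate.
- k = subjects lost to liver-failure death, or transplant for liver failure, with no decline recorded first. This is also an assumption.

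**Three readings of the rate.**
- Observed-case: d/(n − k).
- Safety-set denominator with no rule for the event: d/n.
- Worst status, counting the event as decline: (d + k)/n.

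For n = 20, d = 2, k = 2, with Clopper-Pearson 95% intervals:
- Observed-case: 2/18 = 11.1% (1.4% to 34.7%).
- Safety-set denominator, event uncounted: 2/20 = 10.0% (1.2% to 31.7%).
- Worst status: 4/20 = 20.0% (5.7% to 43.7%).

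A full denominator alone does not help; the event must also be counted.

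**Range with d = 2.**

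| n | k | Observed-case | Worst status | Difference (points) |
|---|---|---|---|---|
| 20 | 1 | 2/19 = 10.5% | 3/20 = 15.0% | 4.5 |
| 20 | 2 | 2/18 = 11.1% | 4/20 = 20.0% | 8.9 |
| 20 | 3 | 2/17 = 11.8% | 5/20 = 25.0% | 13.2 |
| 15 | 1 | 2/14 = 14.3% | 3/15 = 20.0% | 5.7 |
| 15 | 2 | 2/13 = 15.4% | 4/15 = 26.7% | 11.3 |
| 15 | 3 | 2/12 = 16.7% | 5/15 = 33.3% | 16.7 |

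For d from 1 to 3, each lost subject moves the rate by about 4 to 6 points.

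**How many such subjects?** The Background says one-third of the earlier trial's patients had grade 3 toxicity and gives 21 as that group. If 21 is one-third, the trial had about 63 patients (assumption), and 4/63 = 6.3% had progressive dysfunction. That would be 15 × 0.063 ≈ 1.0 subject in 15, or 20 × 0.063 ≈ 1.3 in 20. This is probably an upper-end guide to k. All four were CTP B8 or worse, while section 5.1 requires CTP 7 or lower, and some would have a decline recorded before the event.

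**The case against.** The strongest reply is that the plan leaves a rule unstated and does not adopt a bad one. A reader might infer that 2/18 is the rate the plan prescribes. The documents do not support that. Section 13.1 only bars imputation, and no denominator is set. The safety paragraph of 13.7 ends by assigning its work to the safety set, which could be read as a denominator of all treated subjects. If any post-baseline decline counts, one recorded before death or transplant would still enter the rate.

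A reader might also infer that liver failures vanish from the trial report. They do not. The second half of the 4.5 sentence covers hepatic toxicity, section 11.0 monitors hepatic failure, ascites and encephalopathy, section 17.3 records adverse events through follow-up, and overall survival and time to transplant are estimated. The incidence tables in 13.7 are limited to an undefined on-treatment period, but all safety data are to be listed.

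Nor does the earlier trial show that decline goes unrecorded. Its four patients were recognised as having progressive dysfunction, and the text does not say why two were transplanted.

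These replies reduce the point but do not remove it. The rate itself still has no rule for the event. Early capture is also only partial: the 30-day visit requires blood tests alone, whereas the Background says CTP also needs ascites and encephalopathy graded.

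**Conclusion.** The point holds as a modest one. The rate of CTP class decline and the visit-wise mean changes are undefined where death and transplant intervene, and the natural available-case reading is biased towards apparent safety. The size depends on assumed counts: 11% against 20% in the illustration, with wide and largely overlapping intervals, and about 4 to 6 points per subject lost. Few such subjects are expected under the CTP entry limit. The events are missing from one descriptive secondary rate, not from the report. The study is a non-randomised pilot with no threshold on CTP decline, and the primary endpoint and the 3-of-15 rule are unaffected. The change is worth making because it is cheap and the direction of the bias is known.

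**What to change.** In section 13.7:
- Define CTP decline as worst post-baseline status over the safety set, and count death from liver failure or transplant for liver failure as a decline.
- Exclude liver function and HIDA values obtained after transplant.
- Classify subjects who die of other causes or have a planned transplant on their worst status up to that date, and state how many there are.
- Keep visit-wise mean changes as supplementary. At each visit show the number measured and the reason for each missing value (death, transplant, progression, other).

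Elsewhere:
- Record cause of death and the indication for transplant. The documents do not show that either is already collected. The Background describes radiation as a bridge to transplant, so a planned transplant should not count as liver failure.
- Reconcile the calendar in section 10.0, which marks CTP only at baseline and midway, with the post-treatment CTP endpoint in 4.5.

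The cost is some analysis-plan wording, one or two data fields with a judgement on cause, and possibly a slightly less favourable decline rate. Treatment and sample size do not change.
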